12.3 Long-Term Vital Signs Analyses

Descriptive summaries of actual values and change from baseline to the minimum post-baseline value, maximum post-baseline value, and final value in the long-term analysis period will be summarized for weight, BMI, body temperature, pulse rate, systolic blood pressure and diastolic blood pressure.

Clinically notable vital signs in the long-term analysis period will be identified based on the criteria below. The number and percentage of subjects with at least 1 treatment-emergent value (i.e., not present at baseline) meeting the criteria below will be tabulated, using the worst post-baseline value in either direction.

Clinically Notable Vital Sign Categories

Vital Sign Parameter	Value
Heart rate	≥130 bpm
	<55 bpm
Systolic Blood Pressure	≥160 mg Hg
	≤90 mm Hg

Protocol: TNX-CY-P306 Page 27 of 36

Final v1.0

Diastolic blood pressure	≥100 mg Hg
	≤60 mm Hg

bpm = beats per minute

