#### **8.5.** Concomitant Medications

Many of the restrictions in the lead-in study related to concomitant medications and traumafocused psychotherapy will be relaxed. Therefore, patients may utilize antidepressants, mood stabilizers, anticonvulsants, benzodiazepines, stimulants, and opioids, if needed, unless specifically excluded as outlined below. Patients may take medications to help them sleep, per the judgment of the investigator.

Any concomitant medications or other treatments, including dietary supplements, must be recorded in the patient's medical record and case report form along with the indication, dose and dates of treatment.

The following medications are specifically excluded during the study and patients must agree to refrain from use of these medications during the study:

- Any other forms of cyclobenzaprine (FLEXERIL®, AMRIX®, FEXMID®, or generic equivalents) continue to be specifically excluded during the study and patients must agree to refrain from use of these medications during the study.
- Monoamine oxidase inhibitors (tranylcypromine, phenelzine, isocarboxazid, and selegiline)
- Cytochrome P450 3A4 inhibitors (strong ones only) (refer to Appendix 2 for a list).
- St. John's wort

NOTE: Patients initiating treatment with antidepressants, tramadol or other opioids, triptans, or any other serotonergic medication should be cautioned about the possibility of serotonin syndrome which has been reported in patients receiving cyclobenzaprine with selective serotonin reuptake inhibitors (SSRIs), serotonin–norepinephrine reuptake inhibitors (SNRIs) and other serotoninergic agents. (See Appendix 3, AMRIX® Package Insert, Warnings Section). The patient should be instructed to call the clinic immediately in the event of any of the warning signs or symptoms of serotonin syndrome, as outlined in the informed consent. The investigator should carefully review the patient's complete list of medications when considering new treatments and the site should ask the patient to call the site (or return for an unscheduled clinic visit) within one week after adding a new serotonergic therapy (or increasing the dose of a prior treatment).

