## **10.4.1.4.** Vital Signs

Vital signs (sitting blood pressure and heart rate, respiratory rate, oral temperature, and weight) will be assessed at Visits 1, 3, 4, 5, 6 and 7 (Visit 7 for Track B patients only). Height will be transferred from the lead-in study database for BMI calculations (done at Baseline and Visit 6 for Track A patients or Visit 7 for Track B patients).

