# 12.1. Evaluation of Safety

Safety data will be summarized as a single treatment group receiving 1 or more doses of TNX-102 SL (patients that have taken only 1 tablet of TNX-102 SL will be included).

Safety will be assessed by the monitoring and recording of AEs, clinical laboratory tests, vital signs, visual examination of the oral cavity findings, the monitoring of suicidality using the Columbia C-SSRS scale, and patient-rated assessments of depressive symptomology (BDI-II) and PTSD symptomology (PCL-S).

AEs will be coded using the MedDRA and will be summarized overall and by preferred term and SOC. AEs will also be summarized by severity and relationship to study drug. SAEs and AEs leading to discontinuation of study drug will also be summarized.

Actual values and changes from the extension study baseline values for clinical laboratory test results and vital sign measurements will be summarized at endpoint using descriptive statistics (n, mean, standard deviation (SD), median, minimum, and maximum). Laboratory values will be displayed in the data listings along with corresponding normal ranges, and those that are outside the normal range will be flagged.

Based on the C-SSRS results, the frequency and severity of suicidal ideation and behavior will be tabulated at each time point. The number of patients with baseline and treatment-emergent suicidal ideation and/or suicidal behavior or self-injurious behavior, based on the C-SSRS, will be summarized by treatment group.

All data gathered will be listed by patient and parameter, and clinically significant abnormalities should be recorded as AEs. AEs of special interest indicating potential abuse and dependency will be evaluated and summarized as described in the Statistical Analysis Plan.

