### **18.** APPENDICES

### APPENDIX 1. STUDY DESIGN AND SCHEDULE OF ASSESSMENTS

Period	Baseline	Phone f	Clinic Visits				
Visit	1	2	3	4	5	6	7 j
Study Week	0	2	7	16	28	40	52
Study Day	0	14 ± 3	49 ± 7	112 ± 7	196 ± 7	280 ± 7	$365 \pm 7$
Informed Consent	X						
Inclusion Criteria	X						
Concomitant Medications b	X	Xf	X	X	X	X	X
Vital Signs and weight	Xa		X	X	X	X	X
Inspection of oral cavity c	Xa				X	X i	X
Pregnancy Test d	Xa		X	X	X	X	X
Clinical Laboratory Assessments	Xa				X	X i	X
BDI-II	Xa		X	X	X	X	X
C-SSRS	Xa	X f	X	X	X	X	X
CGI-I (compared to P306 baseline only) e			X	X	X	X	X
PROMIS-Sleep (short form)	Xa		X	X	X	X	X
SDS	Xa		X	X	X	X	X
PCL-S					$X^h$	X h	X
Pharmacogenomic blood draw (optional) g	*	*	*	*	*	*	*
Adverse Events	X	X f	X	X	X	X	X
Telephone Visit		$X^{f}$					
Dispense Study Drug	X		X	X	X	$\mathbf{X}^{\mathrm{j}}$	
Collect/ Count Study Drug Returned			X	X	X	X	X

**Abbreviations:** BDI-II = Beck Depression Inventory-II; C-SSRS = Columbia-Suicide Severity Rating Scales; CGI-I (Clinician Global Impression of Improvement); PROMIS = Patient Reported Outcomes Measurement Information System; SDS = Sheehan Disability Scale; PCL-S = PTSD Checklist-Specific Version

<sup>a These assessments are only to be conducted for patients entering the study from Track B, or Track A patients that roll over into P306 greater than 14 days after the final visit of the previous study.

<sup>b Medications that are ongoing at the end of the previous study will be recorded as such in this study.

<sup>c In addition to the regularly scheduled examination, a visual examination of the oral cavity should be done at any visit in which an oral adverse event has been reported.

<sup>d Women of child-bearing potential only.

<sup>e The CGI-I will be done only in comparison to the baseline visit of P306.

<sup>f Patients enrolled from the double-blind lead-in study, P301/HONOR, only will have the phone check-in.

\*/gThe blood draw for the pharmacogenomic assessment can be obtained at any study visit (including an early termination visit). It should only be obtained one time during the study. Separate written, signed informed consent will be required if the patient is to participate in the optional pharmacogenomic assessment.

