#### Tricyclic Antidepressant-like Effects

Cyclobenzaprine is structurally related to the tricyclic antidepressants, e.g., amitripty-line and imipramine. Tricyclic antidepressants have been reported to produce arrhythline and impramine. Incyclic antidepressants have been reported to produce armyn-mias, sinus tachycardia, prolongation of the conduction time leading to myocardial infarction and stroke [see Contraindications (4)]. AMRIX may enhance the effects of alcohol, barbiturates, and other CNS depressants. Some of the more serious central nervous system (CNS) reactions noted with the tricyclic antidepressants have occurred in short-term studies of cyclobenzaprine for indications other than muscle spasm associated with acute musculoskeletal condi-

tions, and usually at doses somewhat greater than those recommended for skeletal muscle spasm. If clinically significant CNS symptoms develop, consider discontinuation of AMRIX.

uation of AMHIX.

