10.4 Vital Signs

Descriptive summaries (mean, SD, median, minimum, and maximum) of actual values and change from baseline at each assessment time point and last on-treatment assessment will be calculated for vital signs including weight, BMI, body temperature, pulse rate, systolic blood pressure and diastolic blood pressure. 95% confidence intervals will be presented for change from baseline.

These summaries will be presented by assessment time for the Safety Population. ET data will be analyzed with the closest visit that does not have a valid assessment value.

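### Respiratory rate is collected as a vital sign and the protocol promises summaries of vital signs, but the SAP's vital-sign summaries leave it out without declaring the change

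*SAP*

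**What the plan says.** Protocol 10.4.1.4 defines what is measured: "Vital signs (sitting blood pressure and heart rate, respiratory rate, oral temperature, and weight) will be assessed". The readings fall at the in-clinic visits, which are Visit 1 and Visits 3 to 6, with Visit 7 added for Track B. Visit 1 has an exception. Footnote a of the schedule in Appendix 1 begins "These assessments are only to be conducted for patients entering the study from Track B" and then adds Track A patients who roll over more than 14 days after their previous study. Other Track A patients bring their earlier values as baseline.

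Protocol 12.1 sets out the summary. It covers the observed values, and for change it says: "changes from the extension study baseline values for clinical laboratory test results and vital sign measurements will be summarized at endpoint using descriptive statistics". The synopsis says much the same. Neither excepts any vital sign.

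SAP 10.4, which covers the P306 data, plans values and changes at each time point and at the last on-treatment assessment, with 95% confidence intervals for change, for "vital signs including weight, BMI, body temperature, pulse rate, systolic blood pressure and diastolic blood pressure". SAP 12.3, which covers P301, P303 and P306 together, plans changes to the minimum, maximum and final value. These "will be summarized for weight, BMI, body temperature, pulse rate, systolic blood pressure and diastolic blood pressure". Its table of clinically notable values has limits for heart rate, systolic and diastolic pressure only. SAP 13 declares one departure from the protocol, the renumbering of Day 0 as Day 1.

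On co-medication, protocol 8.5 relaxes many lead-in restrictions, so that "patients may utilize antidepressants, mood stabilizers, anticonvulsants, benzodiazepines, stimulants, and opioids", subject to need and to the listed exclusions. The AMRIX label in Appendix 3 states that "AMRIX may enhance the effects of alcohol, barbiturates, and other CNS depressants".

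**The concern.** Long-term safety is the primary objective, and the vital-sign tables are part of how it is met. An analyst who programs from the SAP would produce tables for every vital sign the protocol collects except respiratory rate. The study report would then contain no mean change, interval or extreme-value summary for it, and no statement that this was intended.

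The gap falls at an awkward place. The extension permits drugs that depress the central nervous system alongside a product whose reference label cautions about such combinations. A reader of the safety report could reasonably ask whether breathing rate shifted over the study, and the planned tables would not answer.

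**Working it through.** No figure in the plan needs to be reproduced. The check is a comparison of lists, followed by a count of the readings concerned.

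**Step 1. Collected against summarised.**

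| Measurement | Protocol 10.4.1.4 | SAP 10.4 | SAP 12.3 summaries | SAP 12.3 notable values |
|---|---|---|---|---|
| Blood pressure | yes | yes | yes | yes |
| Heart rate (pulse) | yes | yes | yes | yes |
| Temperature | yes | yes | yes | no |
| Weight | yes | yes | yes | no |
| Respiratory rate | yes | no | no | no |
| BMI | derived, with height from the lead-in | yes | yes | no |

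Five measurements are collected and four reach the summaries. Blood pressure is split into two parameters and BMI is derived, which gives the SAP's six. Respiratory rate is the only one collected and not named.

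**Step 2. Declared or not.** SAP 13 mentions study-day numbering only, so the omission is not declared.

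**Step 3. Where respiratory rate could still appear.** Protocol 12.1 has all data listed by patient and parameter, and SAP 10 plans safety listings. Protocol 12.1 also asks that clinically significant abnormalities be recorded as adverse events. Neither route gives a distribution of values or changes.

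**Step 4. Number of readings.** Inputs: up to 200 patients (protocol 6.2). Post-baseline clinic visits with vital signs are Visits 3 to 6 for Track A, which is 4, and Visits 3 to 7 for Track B, which is 5. Visit 1 is left out of the count because Track A patients who roll over within 14 days are not re-measured then.

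- All Track A: 200 × 4 = 800.
- All Track B: 200 × 5 = 1,000.
- With *a* patients in Track A: 4*a* + 5(200 − *a*) = 1,000 − *a*.

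These are maxima. They assume full enrolment and no dropout or missed visit.

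**Step 5. Is the data there?** For P306 values, yes. Change from baseline in Track A patients who roll over on time needs a respiratory rate from the final visit of the earlier study. The SAP 12.3 summaries need it from P301 and P303 generally. Those protocols are not among the documents, and nothing here says that they recorded it.

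**The case against.** The best case for the plan has four parts.

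- **The wording of SAP 10.4.** Its list opens with *including*, so it could be read as examples, and other SAP sections refer to vital signs without exclusion. This is a fair reading of one word. It is weakened because the list names every other collected vital sign, and SAP 12.3 repeats the same six as a closed list.
- **SAP 12.3 breaks no promise.** The protocol commits to changes from the extension baseline. The pooled analysis in SAP 12 is a selection of additional analyses with its own baseline. This stands. The departure from the protocol is in SAP 10.4; SAP 12.3 confirms how that list was meant and is a secondary place to amend.
- **Nothing is lost.** Listings and adverse-event tables remain, and SAP Appendix 3 gives sedation, somnolence and stupor a display of their own. This stands as far as it goes: respiratory events are still captured and reported. But a listing is not the descriptive summary that the protocol promises, and adverse events depend on investigator judgement. Pulse and blood pressure have those same routes and are summarised as well.
- **The interaction argument is thin.** The label's CNS-depressant warning names alcohol and barbiturates but not opioids or benzodiazepines, and respiratory depression appears only under overdose management. AMRIX is a different formulation. Clinic readings are 7 to 12 weeks apart, and their timing relative to a bedtime dose is not specified. All of this stands. The co-medication setting is a reason to care about the omission; it does not show that respiratory rate would detect an interaction.

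A reader might go further and infer that co-medication is unrestricted, or that the report could say nothing about respiratory safety. The documents support neither. Protocol 8.5 keeps exclusions and leaves sleep medicines to the investigator's judgement, and listings and adverse-event tables are planned.

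**Conclusion.** The point holds as an undeclared gap between protocol and SAP. A vital sign that the protocol collects and says will be summarised is absent from both SAP parameter lists, with no stated reason. At most 800 to 1,000 post-baseline readings in P306 would go unsummarised, on the assumption of 200 patients with complete follow-up; the true number will be lower.

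No analysis is invalidated and no data are lost, but a promised safety summary is dropped where safety is the primary objective. The co-medication context adds relevance, with two limits. The relaxation is shown only against the lead-in study, since the P303 rules are not given. The label warning is general.

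It would also be tempting to say what incidence of abnormal respiratory rate the study could rule out. The documents give no criterion for an abnormal value, so such a bound would describe an undefined event and is not used here.

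**What to change.** - **SAP 10.4:** add respiratory rate to the named parameters, with value and change from baseline by visit and at last on-treatment assessment, and the 95% confidence interval already planned for the others. State how change is handled for Track A patients if the earlier study holds no respiratory rate for them.
- **SAP 12.3:** add it to the minimum, maximum and final-value summaries to the extent that P301 and P303 also collected it. If they did not, say so.
- **Otherwise, SAP 13:** declare the omission and give the reason.

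Whether to add a notable-value criterion, and which, is for the sponsor to settle before the analysis. A repeat of the summary in patients with recorded opioid or benzodiazepine use is optional. It would be uncontrolled and of unknown size, although the coded medication data would allow it.

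The cost is a change of SAP wording and one more parameter in existing tables. The P306 values need no new collection; the pooled summaries and the Track A changes depend on what the earlier studies recorded.

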12.4 Long-Term Clinical Laboratory Evaluations

Descriptive summaries of actual values and change from baseline to the minimum post-baseline value, maximum post-baseline value, and final value in the long-term analysis period will be summarized for chemistry and hematology parameters.

A summary of treatment emergent shifts will compare the baseline L/N/H classification for each laboratory test to the highest and/or lowest L/N/H classification post-baseline in the long-term analysis period.

Additionally, subject counts of any post-baseline elevated alanine aminotransferase (ALT), aspartate aminotransferase (AST), bilirubin, and alkaline phosphatase (ALP) will be presented in a separate table, as follows.

Table 7-1 Elevated Liver Function Test Categories

Clinical Laboratory Parameter	Category
ALT	≥3 × ULN; ≥5 × ULN
AST	≥3 × ULN; ≥5 × ULN
ALT or AST	≥3 × ULN; ≥5 × ULN
ALP	≥1.5 × ULN
Total bilirubin	≥ULN; ≥2 × ULN
Total bilirubin elevation with ALT or AST elevation at any post-baseline timepoint(s)	(ALT or AST ≥3 × ULN) and (total bilirubin ≥2 × ULN)
Concurrent total bilirubin elevation with ALT or AST elevation and ALP <2 × ULN [1] ("potential Hy's law cases")	(ALT or AST \geq 3 × ULN) and ALP $<$ 2 × ULN and (total bilirubin \geq 2 × ULN)

ALP = alkaline phosphatase; ALT = alanine aminotransferase; AST = aspartate aminotransferase; ULN = upper limit of normal

Potential Hy's law cases (based on the recommendation in "Guidance for Industry Drug-Induced Liver Injury: Premarketing Clinical Evaluation") will be identified as subjects with post-baseline ALT or AST \geq 3 x upper limit of normal (ULN) and total bilirubin \geq 2 x ULN and ALP <2 × ULN on the same date, as noted above. Liver function test data on any subjects with ALT or AST \geq 3 × ULN will be listed, and any potential Hy's law cases will be specifically identified.

To assess cases potentially meeting requirements for Hy's Law, an evaluation of druginduced serious hepatotoxicity plot of bilirubin against peak ALT will be generated by treatment group, as described by Watkins et al (2008). This plot will be reproduced for

^[1] Concurrent means on the same date.

Protocol: TNX-CY-P306 Page 28 of 36

Final v1.0

peak AST vs. peak total bilirubin, as well as for the greater of peak AST and peak ALT vs. peak total bilirubin.

Protocol: TNX-CY-P306 Page 29 of 36

Final v1.0

12.5 Long-Term Exposure

Summary statistics will be presented for duration of exposure (days and weeks) in the long-term analysis period, defined as the [last dose date of TNX-102 SL – first dose date of TNX-102 SL + 1], for TNX-102 SL. Duration of treatment (weeks) will also be summarized as categorical measures (eg, 0-12 weeks, \ge 12 – 24 weeks, \ge 24 – 36 weeks, \ge 36 – 48 weeks, and \ge 48 weeks).

13. CHANGES FROM PLANNED ANALYSIS

Study day as it appears in data listings and the Study Data Tabulation Model (SDTM) and Analysis Data Model (ADaM) datasets will differ from the protocol: The protocol describes the day of first dose as "Day 0"; the listings and datasets will conform to the standard of first dose day appearing as "Day 1".

Protocol: TNX-CY-P306 Page 30 of 36

Final v1.0

15. APPENDICES

15.1 Appendix 1

The following reporting conventions will be adopted for the presentation of study data. These conventions will enhance the review process and help to standardize presentation with common notations.

15.1.1 General Reporting Conventions

- All tables and data listings will be developed in Landscape Orientation, unless presented as part of the text in a clinical study report (CSR).
- Figures will be presented in Landscape Orientation, unless presented as part of the text in a CSR.
- Legends will be used for all figures with more than one variable or item displayed.
- Figures will be in black and white, unless color figures have been identified as useful for discriminating presentation in the figure. Lines in figures should be wide enough to view the line after being photocopied.
- Specialized text styles, such as bolding, italics, borders, shading, superscripted and subscripted text will not be used in tables, figures, and data listings unless they add significant value to the table, figure, or data listing.
- Only standard keyboard characters should be used in tables and data listings. Special characters, such as non-printable control characters, printer specific, or font specific characters, will not be used on a table, figure, or data listing. Hexadecimal character representations are allowed (e.g., μ , α , β).
- All titles will be centered on a page. The ICH numbering convention is to be used for all tables, listings, and graphs (TLGs).
- All footnotes will be left justified at the bottom of a page. Footnotes must be present on the page where they are first referenced. Footnotes should be used sparingly and must add value to the TLG. If more than four footnote lines are planned then a cover page may be used to display footnotes.
- Missing values for both numeric and character variables will be presented as blanks in a table or data listing. A zero (0) may be used if appropriate to identify when the frequency of a variable is not observed.
- All date values will be presented as YYYY-MM-DD (e.g., 2001-10-17) format. A four-digit year is preferred for all dates.
- All observed time values will be presented using a 24-hour clock HH:MM:SS format (e.g., 01:35:45 or 11:26). Seconds should only be reported if they were measured as part of the study.
- Time durations will be reported in mixed HHhr MMm SSs notation (e.g., 5h 32m, or 27h 52m 31s). The use of decimal notation to present (display) time

Protocol: TNX-CY-P306 Page 32 of 36

Final v1.0

durations should be avoided (e.g. 0.083h = 5m) unless it is necessary to show the computation of time differences in a table, figure, or data listing, in which case both notations may be used to display the time duration.

- All TLGs will have the name of the program, location, programmer, and a date stamp on the bottom of each output.
- All analysis programs developed for a TLG display will be self-contained to facilitate transfer of programs to multiple computing environments and transfer to a regulatory agency (if requested).

